### 3.6.3. Selection of Data in the Event of Multiple Records in an Analysis Window

Depending on the statistical analysis method, single values may be required for each analysis window. For example, change from baseline by visit usually requires a single value, whereas a time-to-event analysis would not require 1 value per analysis window.

If multiple valid nonmissing numeric observations exist in an analysis window, records will be chosen based on the following rules if a single value is needed:

- For baseline, the last available record on or prior to the date of the first dose of study drug will be selected. If there are multiple records with the same time or no time recorded on the same day, average (arithmetic mean) will be used for the baseline value.
- For postbaseline visits:
  - The record closest to the nominal day for that visit will be selected except for HCV RNA posttreatment follow-up visits, for which the latest record in the analysis window will be selected.
  - If there are 2 records that are equidistant from the nominal day, the later record will be selected.
  - If there is more than 1 record on the selected day, the average will be taken, unless otherwise specified.

If multiple valid nonmissing categorical observations exist in a window, records will be selected as follows:

- For baseline, the last available record on or prior to the date of the first dose of study drug will be selected. If there are multiple records with the same time or no time recorded on the same day, the value with the lowest severity will be selected (eg, normal will be selected over abnormal). If multiple ECG measurements occur on the same day prior to the first dose of any study drug, the value with the lowest severity will be selected regardless of the timing of these multiple ECG measurements.
- For postbaseline visits, follow the same rules described above for postbaseline numeric observations, except that if there are multiple records on the same day, the most conservative value will be selected (eg, abnormal will be selected over normal).

## 4. SUBJECT DISPOSITION

### 4.1. Subject Enrollment and Disposition

A summary of subject enrollment will be provided for each country and investigator. The summary will present the number and percentage of subjects in the Safety Analysis Set. For each column, the denominator for the percentage calculation will be the total number of subjects analyzed for that column.

A summary of subject disposition will be provided by genotype and treatment group. This summary will present the number of subjects screened, the number of subjects not enrolled, the number of subjects enrolled, the number of subjects enrolled but never treated, the number of subjects enrolled and treated (ie, safety analysis set), in FAS, and the number and percentage of subjects in each of the categories listed below. The denominator for the percentage calculation will be the total number of subjects in the Safety Analysis Set for each column.

- Continuing study treatment (if applicable)
- Completed study treatment
- Did not complete study treatment with reasons for premature discontinuation of study treatment
- Completed study
- Did not complete the study with reasons for premature discontinuation of study

Among subjects who completed study treatment and who discontinued study treatment, the number and percentage of subjects will be summarized for:

- Who had no HCV posttreatment Week 4 assessment and thereafter (No HCV FU-4 Assessment and thereafter)
- Who had HCV posttreatment Week 4 assessment but no HCV posttreatment Week 12 and thereafter (With HCV FU-4 but No FU-12 and thereafter)

If a subject did not have any HCV RNA assessment  $\geq$  21 days after the last dose of any study drug (ie, lower bound of FU-4 visit for HCV RNA data), the subject is categorized as having “No HCV FU-4 and thereafter.” If a subject had the HCV FU-4 assessment but did not have any HCV RNA assessment  $\geq$  70 days after the last dose of any study drug (ie, lower bound of FU-12 visit for HCV RNA data), the subject is categorized as having “With HCV FU-4 but No FU-12 and thereafter.”

In addition, the total number of subjects who were enrolled, and the number of subjects in each of the disposition categories listed above will be depicted by a flowchart.

The following by-subject listings will be provided by subject ID number in ascending order to support the above summary tables:

- Disposition for subjects who complete study treatment and study
- Disposition for subjects who did not complete study treatment and/or study with reasons for premature discontinuation of study treatment and/or study
- Lot number and kit ID (if applicable)

#### **4.2. Extent of Exposure**

Extent of exposure to study drug will be examined by assessing the total duration of study drug exposure and the level of adherence to the study drug regimen specified in the protocol.

##### **4.2.1. Duration of Exposure to Study Drug**

Total duration of exposure to study drug will be defined as last dose date minus first dose date plus 1, regardless of any temporary interruptions in study drug administration, and will be expressed in weeks using up to 1 decimal place (eg, 4.8 weeks). The total duration of exposure to study drug will be summarized using descriptive statistics (n, mean, SD, median, Q1, Q3, minimum, and maximum) and using the number (ie, cumulative counts) and percentage of subjects exposed through the following time periods: Baseline (Day 1), Week 4 (Day 28), Week 8 (Day 56), Week 12 (Day 84), Week 16 (Day 112), Week 20 (Day 140), and Week 24 (Day 168). A 3-day window is applied to the last planned on-treatment visit to match with the protocol-specified visit window, i.e. number of subjects exposed through Week 8 will be calculated as the number of subjects who were exposed to study drug for at least 53 days. Number of subjects exposed through week 12 will be calculated as the number of subjects who were exposed to study drug for at least 81 days. Number of subjects exposed through week 24 will be calculated as the number of subjects who were exposed to study drug for at least 165 days.

##### **4.2.2. Adherence to Study Drug**

The presumed total number of tablets administered to a subject will be determined by the data collected on the drug accountability CRF using the following formula:

$$\begin{aligned} \text{Total Number of Doses Administered} = \\ (\sum \text{No. of Tablets Dispensed}) - (\sum \text{No. of Tablets returned}) \end{aligned}$$

The level of adherence to the study drug regimen will be assessed based on the total amount of study drug administered relative to the total amount of study drug prescribed at baseline.

The level of adherence will be expressed in percentage using the following formula:

$$\text{Level of Adherence}(\%) = \left( \frac{\text{Total Amount of Study Drug Administered}}{\text{Total Amount of Study Drug Prescribed at baseline}} \right) \times 100$$

Note: If calculated adherence is greater than 100%, the result will be set to 100%.

In this study, the total amount of LDV/SOF prescribed for 8 weeks would require 56 tablets, for 12 weeks would require 84 tablets, and for 24 weeks would require 168 tablets.

Subjects who prematurely discontinue study drug for lack of efficacy (ie, virologic failure) will have the total amount of study drug prescribed calculated up to the first date when virologic failure criteria were met. For virologic failure confirmed by 2 consecutive measurements, the date of the first measurement will be used. If study drug bottles are dispensed on or after the subject first met virologic failure criteria, these bottles will not be included in the calculation of adherence. If a bottle is dispensed and the bottle is returned empty, then the number of tablets returned will be entered as zero. If a bottle is dispensed but not returned (missing), the number of tablets taken from that bottle will be counted as zero.

Descriptive statistics for the level of adherence (n, mean, SD, median, Q1, Q3, minimum, and maximum) with the number and percentage of subjects belonging to adherence categories (eg, {< 80%, ≥ 80 to < 90%, ≥ 90%}) will be provided by treatment group for the Safety Analysis Set. Categorical displays also will be provided for the number of subjects who are at least 80% adherent to their drug regimen (ie, adherence is ≥ 80% for the study drugs).

No inferential statistics will be provided for duration of exposure and adherence to study drug.

A separate by-subject listing of study drug administration and drug accountability will be provided by subject ID number (in ascending order) and visit (in chronological order).

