3.4.2. Virologic Response Base Stopping Criteria

The following on-treatment virologic response-based treatment stopping criteria will be utilized:

- Confirmed HCV RNA \geq LLOQ after 2 consecutive HCV RNA $<$ LLOQ
- Confirmed $> 1 \log_{10}$ increase from on-treatment nadir
- HCV RNA \geq LLOQ at Week 8

Confirmation should be performed as soon as possible and must occur no later than 2 weeks after an initial observation indicating virologic failure during the on-treatment phase. All subjects who terminate treatment early will complete the ET visit and posttreatment Week 4 and 12 visits.

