6.3. Treatment Assessments

6.3.1. Week 2 (\pm 3 days): Group 1, 2, and 3

The following procedures/assessments are to be completed at the end of Week 2:

- Obtain vital signs
- Assessment of AEs and concomitant medications

- Obtain blood samples for:
 - Hematology
 - Chemistry
 - HCV RNA
 - Viral sequencing/phenotyping
 - Sparse PK sample
- Assess adherence with study drug dosing regimen including pill count

6.3.2. Week 4 (\pm 3 days): Group 1, 2, and 3

The following procedures/assessments are to be completed at the end of Week 4:

- Obtain vital signs
- Assessment of AEs and concomitant medications
- Conduct pregnancy prevention counselling
- Obtain blood samples for:
 - Hematology
 - Chemistry
 - HCV RNA
 - Viral sequencing/phenotyping
 - Sparse PK sample
 - Serum β -hCG pregnancy test for females of childbearing potential only
 - HIV-1 RNA and CD4 cell count will only be collected and analyzed for HIV co-infected subjects
 - HBV DNA (only in subjects who are HBcAb+ at Screening)
- Assess adherence with study drug dosing regimen including pill count
- Dispense study drug as directed by the IWRs

6.3.3. Week 6 (\pm 3 days): Group 1, 2, and 3

The following procedures/assessments are to be completed at the end of Week 6:

- Obtain vital signs
- Assessment of AEs and concomitant medications
- Obtain blood samples for:
 - Hematology
 - Chemistry
 - HCV RNA
 - Viral sequencing/phenotyping
 - Sparse PK sample
 - Intensive PK (for subjects who have consented)
 - Hemodialysis PK (for subjects who have consented)
- Assess adherence with study drug dosing regimen including pill count

6.3.4. Week 8 (\pm 3 days): Group 2 and 3 (For Group 1 Week 8, see End of Treatment Visit)

The following procedures/assessments are to be completed at the end of Week 8 for Groups 2 and 3 only:

- Obtain vital signs
- Assessment of AEs and concomitant medications
- Conduct pregnancy prevention counselling
- Obtain blood samples for:
 - Hematology
 - Chemistry
 - HCV RNA
 - Viral sequencing/phenotyping

- Sparse PK sample
- Serum β-hCG pregnancy test for females of childbearing potential only
- HIV-1 RNA and CD4 cell count will only be collected and analyzed for HIV co-infected subjects
- HBV DNA (only in subjects who are HBcAb+ at Screening)
- Intensive PK (for subjects who have consented)
- Hemodialysis PK (for subjects who have consented)
- Assess adherence with study drug dosing regimen including pill count
- Dispense study drug as directed by the IWRs

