### **3.3. Examination of Subject Subsets**

Subject subsets within each genotype will also be explored by baseline characteristics for the primary efficacy endpoint, SVR12. The baseline characteristics include the following:

- age (< 65 years,  $\geq$  65 years)
- sex (male, female)
- cirrhosis (presence, absence)
- prior HCV treatment experience (treatment naive, treatment experienced)
- prior HCV treatment for treatment experienced subjects [DAA Naive (Peg-IFN + RBV, Other)]
- HCV genotype
- baseline HCV RNA (< 800,000 IU/mL,  $\geq$  800,000 IU/mL)
- baseline body mass index (BMI) (< 30 kg/m^2,  $\geq$  30 kg/m^2)
- baseline alanine aminotransferase (ALT) ( $\leq$  1.5  $\times$  upper limit of normal (ULN),  $>$  1.5  $\times$  ULN)

- IL28B (CC, non-CC; with non-CC further broken down to CT, TT)
- type of current dialysis (Hemodialysis, Peritoneal Dialysis)
- adherence to study regimen (< 80%, ≥ 80%)

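### For subjects who stop for virologic failure, SAP 4.2.2 cuts prescribed tablets by date but administered tablets only by bottle, so tablets taken after the first failing sample from bottles already in hand can inflate adherence

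*SAP*

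**What the plan says.** SAP 4.2.2 defines adherence as tablets administered divided by tablets prescribed at baseline, with results above 100% set to 100%. For the administered amount, "The presumed total number of tablets administered to a subject will be determined by the data collected on the drug accountability CRF", as dispensed minus returned.

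Subjects who stop early for virologic failure have a special rule. They "will have the total amount of study drug prescribed calculated up to the first date when virologic failure criteria were met", and "For virologic failure confirmed by 2 consecutive measurements, the date of the first measurement will be used". One limit applies to the administered amount: "If study drug bottles are dispensed on or after the subject first met virologic failure criteria, these bottles will not be included". A bottle that is never returned counts as zero tablets taken.

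Protocol 3.4.2 says that confirmation should be done as soon as possible and "must occur no later than 2 weeks after an initial observation indicating virologic failure during the on-treatment phase". In the Protocol Appendix 2 tables, drug is dispensed at Day 1 and Week 4 in all groups, at Week 8 in Groups 2 and 3, and at Weeks 12, 16 and 20 in Group 3. HCV RNA is drawn at Week 6, but no drug is dispensed then.

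SAP 3.3 lists adherence, split at 80%, among the subsets for SVR12.

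**The concern.** The two terms of the ratio cover different periods. The denominator stops on the day of the first failing sample. The numerator stops only at the last bottle dispensed before that day, and it includes whatever was taken from that bottle afterwards. The bottle exclusion suggests that drug taken after failure was meant to be left out, but it does this only in part.

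At stake is how a failure is described. A subject below 80% up to the failing sample may appear in the adherent row of the SVR12 subgroup display. Such a subject is by definition not an SVR12 success, so the move lowers SVR12 in the adherent row and raises it in the other. Rows within genotype may be small. As an assumption, if the below-80% row holds 2 to 10 subjects, of whom this is the only failure, removing that subject raises the row's SVR12 from between 1/2 (50%) and 9/10 (90%) to 100%.

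**Working it through.** **Inputs.** One tablet daily (Protocol 5.3); bottles of 28 or 30 tablets (Protocol 5.2.2); dispensing visits as above; up to 14 days to confirmation (Protocol 3.4.2). Assumed: one bottle per four weeks, all bottles returned, and dosing continued for 0 to 14 days after the first failing sample.

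**The plan's own figures.** 7 × 8 = 56, 7 × 12 = 84 and 7 × 24 = 168 tablets, as SAP 4.2.2 states.

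**Formulas.** Let D be the day of the first failing sample, a the tablets taken up to D, and b the tablets taken after D from bottles dispensed before D.
- As written: min(100%, (a + b)/D)
- Same period in both terms: a/D

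**Failure first seen at Week 6 (D = 42).** The protocol's first stopping criterion needs two consecutive results below LLOQ beforehand. On the visit schedule these are Weeks 2 and 4, so Week 6 is the first scheduled visit at which it can be met. The Week 4 bottle stays in the numerator.

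| a | a/42 | as written, b = 7 | as written, b = 14 |
|---|---|---|---|
| 20 | 47.6% | 27/42 = 64.3% | 34/42 = 81.0% |
| 27 | 64.3% | 34/42 = 81.0% | 41/42 = 97.6% |
| 28 | 66.7% | 35/42 = 83.3% | 42/42 = 100% |
| 33 | 78.6% | 40/42 = 95.2% | 47/42, capped to 100% |

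With b = 0 nothing is distorted. Since 33/42 is below 80% and 34/42 is above it, the category changes only for a = 27 to 33 when b = 7, and for a = 20 to 33 when b = 14. Bottles of 28 or 30 tablets give the same result. The last column cannot apply to Group 1: 42 + 14 = 56 is planned completion, and the special rule covers only early stopping.

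These rows assume that every dose after the failing sample is taken. At an unchanged rate r, the reported value is r × 49/42 (7 days) or r × 56/42 (14 days). It reaches 80% from r = 68.6% or r = 60.0% respectively. For example, 28/42 plus about 5 of 7 gives 33/42 = 78.6%, which does not cross; 28/42 plus about 9 of 14 gives 37/42 = 88.1%, which does.

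**Failure first seen at a dispensing visit.** The new bottle is excluded, so b can come only from left-over tablets. A true 75% stays at 75% if these are returned or unused. If they are kept and taken for up to 14 days (28-tablet bottles):
- Week 4: (21 + 7)/28 = 100%
- Week 8: (42 + 14)/56 = 100%
- Week 12: (63 + 14)/84 = 91.7%
- Week 16: (84 + 14)/112 = 87.5%
- Week 20: (105 + 14)/140 = 85.0%

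**The case against.** The strongest reply is that the SAP already guards against this. Every bottle dispensed on or after first failure is dropped, and most visits from Week 4 on are dispensing visits for subjects still on treatment. This stands as a limit on scope: the clear case is Week 6 or an unscheduled visit, with dosing continued until confirmation. The documents set an outer limit for confirmation but do not say how long dosing lasts in practice. The guard does not remove the mismatch for a bottle already in hand.

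Second, the unreturned-bottle rule works the other way. A fully adherent Week 6 failure whose Week 4 bottle of 28 is missing is reported at 28/42 = 66.7%. That is true, but it is a separate error and does not correct this one for a subject who returns bottles.

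Third, the consequence is small. Adherence carries no inferential statistics, the split is one of twelve subsets, and the SAP provides accountability listings by subject and visit, so individual cases can be inspected. This stands too, and it limits the importance of the point.

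A reader might infer that every tablet taken after failure is kept in the numerator, or that the adherence category is wrong for every subject affected. The documents support neither. The bottle exclusion rules out the first. For the second, a category changes only when a threshold is crossed; a subject with 42/42 is capped at 100%, which is correct.

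**Conclusion.** The rule is wrong as written, with small impact. For a subject who stops for on-treatment virologic failure and takes further tablets from a bottle dispensed before the first failing sample, reported adherence is too high: by 7/42 = 16.7 percentage points for 7 extra tablets at Week 6, and by 14/42 = 33.3 points for 14, before the cap. This rests on dosing continuing after that sample and on bottles being returned.

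Few subjects are likely to be affected. Protocol 1.2.2.4 reports no on-treatment virologic failure among 20 subjects in the earlier renal impairment study (exact 95% upper limit 1 − 0.025^(1/20) = 16.8%). That is only a rough guide, because those subjects received sofosbuvir plus ribavirin and had severe renal impairment.

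A reader might also infer that the efficacy result is biased. It is not: overall SVR12 is unchanged. Only the placing of such a subject in the adherence summaries and in the SVR12 adherence subgroup can be wrong.

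**What to change.** Use one period for both terms. For subjects who stop early for virologic failure, run the prescribed amount from the first dose to the last dose date defined in SAP 3.6.1, and count all dispensed bottles. The bottle exclusion must go at the same time. Otherwise a Week 8 failure in Group 2 who took 56/56 and then 14 tablets from the new bottle would score 56/70 = 80.0% instead of 70/70.

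Under this rule the Week 6 examples become (27 + 7)/49 = 69.4%, (33 + 7)/49 = 81.6% and, with 14 extra tablets, (20 + 14)/56 = 60.7%. The 81.6% is a true figure for the whole dosing period, not an artefact.

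Alternatively, where the accountability data hold a tablet count at the first failing visit, end both terms on that date. Protocol 6.3.3 requires sites to "Assess adherence with study drug dosing regimen including pill count" at Week 6, but neither document shows that the count of a bottle still in use is entered on the accountability form. Check this before choosing that option.

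The cost is about two sentences in SAP 4.2.2 and a small programming change, with no new data for the last-dose option. The downside is slightly less favourable reported adherence for some virologic failures.

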5.2.2. Packaging and Labeling

LDV/SOF FDC tablets are packaged in white, high density polyethylene (HDPE) bottles. Each bottle contains either 28 or 30 tablets, a silica gel desiccant canister and polyester packing material. Each bottle is enclosed with a white, continuous thread, child-resistant screw cap with an induction-sealed, aluminum-faced liner.

All LDV/SOF FDC bottles to be distributed to centers in the EU, North America and Asia Pacific shall be labelled to meet all applicable requirements of the US Food and Drug Administration (FDA), Annex 13 of Good Manufacturing Practices: Manufacture of investigational medicinal products and local regulations as applicable.

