6.3.5. Week 12, 16, and 20 (± 3 days): Group 3 (For Group 2 Week 12, see End of Treatment Visit)

The following procedures/assessments are to be completed at the end of Week 12, 16, and 20 for Group 3 only:

- Obtain vital signs
- Assessment of AEs and concomitant medications
- Conduct pregnancy prevention counselling
- Obtain blood samples for:
 - Hematology
 - Chemistry
 - HCV RNA
 - Viral sequencing/phenotyping
 - HIV-1 RNA and CD4 cell count will only be collected and analyzed for HIV co-infected subjects
 - HBV DNA (only in subjects who are HBcAb+ at Screening)
 - Sparse PK sample

- Serum β -hCG pregnancy test for females of childbearing potential only
- Week 12 only: Intensive PK (for subjects who have consented)
- Week 12 only: Hemodialysis PK (for subjects who have consented)
- Assess adherence with study drug dosing regimen including pill count
- Dispense study drug as directed by the IWRS

6.3.6. End of Treatment Visit: Group 1 Week 8 (\pm 3 days), Group 2 Week 12 (\pm 3 days), Group 3 Week 24 (\pm 3 days) or Early Termination (ET)

The following procedures/assessments are to be completed at the end of Week 24/ET:

- Perform complete physical examination, including vital signs and body weight
- Perform 12-lead ECG
- Assessment of AEs and concomitant medications
- Pregnancy prevention counseling
- Subject completes Health Related Quality of Life Questionnaire: SF-36, CLDQ-HCV, FACIT-F, and WPAI
- Obtain blood samples for:
 - Hematology
 - Chemistry
 - Coagulation tests
 - HCV RNA
 - Viral sequencing/phenotyping
 - HIV-1 RNA and CD4 cell count will only be collected and analyzed for HIV co-infected subjects
 - HBV DNA (only in subjects who are HBcAb+ at Screening)
 - Sparse PK sample
 - Serum β -hCG pregnancy test for females of childbearing potential only

- CCI
- Group 1, Week 8: Intensive PK (for subjects who have consented)
- Group 1, Week 8: Hemodialysis PK (for subjects who have consented)
- Group 2, Week12: Intensive PK (for subjects who have consented)
- Group 2, Week 12: Hemodialysis PK (for subjects who have consented)
- Assess adherence with study drug dosing regimen including pill count
- Subjects should return all bottles of study drug

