#### 6.1.3. Subgroup Analysis of the Primary Efficacy Endpoint

The point estimates and 95% exact CIs of the SVR12 rates will be displayed by genotype for subgroups outlined in Section [3.3](#).

SVR12 rates will be summarized by categories of early viral response to explore possible early on-treatment predictors of SVR12. The relationship between SVR12 and study drug interruption may also be explored. A forest plot will graphically present estimates and 95% CIs in SVR12 rates for each of the subgroups.

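### Scoring an unreturned bottle as zero tablets can put fully adherent 8- and 12-week subjects below 80% but not 24-week subjects, and the adherence denominator depends on why a subject stopped

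*SAP*

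**What the plan says.** SAP 4.2.2 computes tablets taken as dispensed minus returned, then overrides that formula for a bottle that never comes back: "If a bottle is dispensed but not returned (missing), the number of tablets taken from that bottle will be counted as zero". Adherence is the "total amount of study drug administered relative to the total amount of study drug prescribed at baseline", capped at 100%. On the denominator, "the total amount of LDV/SOF prescribed for 8 weeks would require 56 tablets, for 12 weeks would require 84 tablets, and for 24 weeks would" need 168.

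There is one exception to the full-course denominator. Subjects who stop early for virologic failure "will have the total amount of study drug prescribed calculated up to the first date when virologic failure criteria were met". Subjects who stop early for any other reason keep 56, 84 or 168.

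The result is used twice. SAP 4.2.2 tabulates adherence categories by treatment group. SAP 3.3 includes, in a list introduced as baseline characteristics, the entry beginning "adherence to study regimen (< 80%, ≥ 80" as a subset for SVR12. SAP 6.1.3 adds: "The point estimates and 95% exact CIs of the SVR12 rates will be displayed by genotype for subgroups outlined in Section" 3.3.

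On supply, Protocol 5.2.2 says "Each bottle contains either 28 or 30 tablets", and Protocol 6.3 tells sites to "Dispense study drug as directed by the IWRS". Protocol 5.5 requires all used and unused drug to come back to the site.

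**The concern.** A bottle is a fixed number of tablets, but the three courses differ threefold in length. A rule that writes off a whole bottle therefore costs an 8-week subject a much larger share of the course than a 24-week subject, while the 80% cut is the same for all. An adherence difference between treatment groups could then reflect course length and nothing the subjects did.

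The SVR12 subgroup inherits this. Genotype 1 subjects can be in any of the three groups (SAP 1.2), so a genotype column can pool all three durations. Within such a column a lost bottle moves non-cirrhotic 8- and 12-week subjects below 80% more readily than cirrhotic 24-week subjects, so adherence is mixed with cirrhosis and duration.

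The virologic-failure exception adds a second problem. On-treatment virologic failures are SVR12 failures. Giving them, and only them, a shortened denominator makes the stratum depend partly on the outcome that the subgroup is meant to describe.

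**Working it through.** **1. The plan's denominators.** One tablet daily (Protocol synopsis) × 7 days × 8, 12 or 24 weeks = 56, 84 and 168. These agree with SAP 4.2.2.

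**2. Bottles per course.** Protocol Appendix 2 shows dispensing at Day 1 and Week 4 in Group 1 (2 occasions), also at Week 8 in Group 2 (3), and also at Weeks 12, 16 and 20 in Group 3 (6). One bottle per occasion fits the bottle size and the four-week interval, but the documents do not state it. It is an assumption here.

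**3. Every tablet taken, one 28-tablet bottle not returned.**

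- Group 1: (56 − 28)/56 = 28/56 = 50.0%
- Group 2: (84 − 28)/84 = 56/84 = 66.7%
- Group 3: (168 − 28)/168 = 140/168 = 83.3%

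Group 3 falls below 80% only when two bottles are lost: 112/168 = 66.7%.

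**4. With 30-tablet bottles.** If bottles are emptied in turn, the lowest score arises from losing a full bottle and the highest from losing the last, partly used one.

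- Group 1: 26/56 = 46.4% to 30/56 = 53.6%
- Group 2: 54/84 = 64.3% to 60/84 = 71.4%
- Group 3: 138/168 = 82.1% to 150/168 = 89.3%

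No group changes sides of 80%.

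**5. How often a fully adherent subject would be scored below 80%.** Let q be the chance that a bottle is not returned, independent between bottles. The documents give no value, so q is assumed. Groups 1 and 2 need at least one loss: 1 − (1 − q)² and 1 − (1 − q)³. Group 3 needs at least two: 1 − (1 − q)⁶ − 6q(1 − q)⁵.

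| q (assumed) | Group 1 | Group 2 | Group 3 |
|---|---|---|---|
| 1% | 2.0% | 3.0% | 0.1% |
| 3% | 5.9% | 8.7% | 1.2% |
| 5% | 9.8% | 14.3% | 3.3% |
| 10% | 19.0% | 27.1% | 11.4% |

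Group 3 is least affected at every value.

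**6. Reason for stopping.** Take a Group 3 subject who stops at Day 56 having taken every tablet. After an adverse event the score is 56/168 = 33.3%. If virologic-failure criteria were first met on that day, it is 56/56 = 100%. Drug intake is identical, but the strata are opposite.

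**7. Share of the below-80% stratum due to lost bottles.** Let d be the proportion stopping before 80% of the course without virologic failure (also assumed), and p the probability from step 5. With no other source of non-adherence, the share is (1 − d)p / [(1 − d)p + d]. Over d from 2% to 20% and q from 1% to 10%, it runs from about 1% (Group 3, d = 20%, q = 1%) to 93% (Group 2, d = 2%, q = 10%).

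**The case against.** Three parts of the case for the plan stand.

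- **Definition.** The SAP measures adherence against the prescribed course. A subject who stops for an adverse event did receive less of it, so a low score is what the definition intends. Not every such stop falls below 80% either: 45 of 56 tablets is 80.4%.
- **Virologic failure.** Protocol 3.4 requires drug to be discontinued after virologic failure. A full-course denominator would let the failure itself push subjects below 80%. A virologic-failure stopper who skipped doses can still score below 80%. The exception has a rationale; what remains is the unequal treatment of stoppers with the same drug intake.
- **Limited reach.** The subgroup is exploratory, and no inferential statistics are planned for adherence. SAP 4.1 reports treatment completion with reasons, SAP 6.2.2 splits relapse by completion of study drug, and a by-subject accountability listing would help a reader trace missing bottles. That listing does not correct the table or the forest plot.

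Two other defences stand only in part. Counting lost bottles as zero is conservative for reporting an adherence rate, but not for sorting subjects into strata. SAP 3.2 groups efficacy analyses by genotype and treatment group; splitting the subgroup columns by treatment group would end the pooling of durations but not the misclassification.

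A reader might go further and infer that the below-80% stratum is mostly an artefact, or that SVR12 by adherence cannot be interpreted at all. The documents do not support this. They give neither a bottle-loss nor an early-stop rate. With q = 3% and d = 20%, the lost-bottle share is about 19%, 26% and 5% in Groups 1, 2 and 3, a minority in each. That 20% is the discontinuation rate in the earlier study in Protocol 1.2.2.2 (4 of 20, on another regimen in severe renal impairment), so it serves only as a range check.

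**Conclusion.** The point holds as a minor one. Given one bottle per dispensing, a single unreturned bottle is enough to misclassify a fully adherent Group 1 or Group 2 subject as below 80%, but not a Group 3 subject. This holds for either bottle size. Separately, the shortened denominator for virologic failure alone makes membership of the SVR12 adherence subgroup depend partly on an outcome-related reason for stopping.

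The direction of the lost-bottle effect follows from the SAP's rule and the course lengths. Its frequency does not: the table in step 5 rests on an assumed, independent non-return rate, and the share in step 7 also rests on an assumed early-stop rate. The adherence table by treatment group and one descriptive subgroup are affected. The primary SVR12 estimate and its confidence interval are not.

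**What to change.** In SAP 4.2.2, add a second adherence version. Where a bottle is not returned, remove its tablets from the numerator and the same number of prescribed tablets from the denominator. One lost 28-tablet bottle then gives 28/28, 56/56 and 140/140, which is 100% in every group for a fully adherent subject. The existing cap deals with surplus tablets from 30-tablet bottles. If no bottle is returned, this version should be reported as missing. Keep the count-as-zero version as the lower bound.

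For SVR12 by adherence, show the result under both versions, and add one display that applies a single denominator rule to all early stoppers whatever the reason. Dividing tablets counted by days from first to last dose is not enough alone: a Group 1 subject with one lost bottle still scores 28/56 = 50% unless that bottle's days are also removed.

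In SAP 3.3, list adherence as a post-baseline exploratory subset, apart from the baseline characteristics.

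The cost is SAP wording and one or two derived variables, with no new data. Adherence will be slightly overstated where an unreturned bottle was really unused; the retained lower bound shows by how much.
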